## BACKGROUND

Chronic obstructive pulmonary disease (COPD) results in nearly 750,000 hospitalizations annually and is the third leading cause of 30-day hospital readmissions in the United States. Improving the quality of care for hospitalized COPD patients has recently become a national priority through the Centers for Medicare and Medicaid Services' Hospital Readmissions Reduction Program. A key element of improving care quality is translating existing evidence into improved practice. Extensive evidence exists to support the efficacy of inhaled medications to control and reduce COPD symptoms and to improve patient outcomes. However, the real-world effectiveness of these medications is often limited due both to poor inhaler technique and to insufficient adherence to treatment plans. Most interventions for hospitalized patients with COPD focus on medication reconciliation, treatment optimization, and inhaler technique education prior to being discharged home. However, after discharge home, patients quickly lose inhaler technique skills, have difficulty adhering to complex regimens, and lack tools to aid adherence, such as lung function response to their treatment regimen. Interventions to reinforce skills and support adherence are needed across care transitions to reduce the risk of deleterious health outcomes.

Simple and feasible at-home interventions to provide skills training and adherence support are needed. Our novel idea is to pair at-home inhaler skill training with at-home spirometry measurements to comprehensively support both medication skill and adherence. I propose testing a novel at-home self-management support program called "BREATHES" (Bringing Respiratory Education for improved Adherence and Technique Home through E-interventions for Self-management) Program. BREATHES will include two main components: first, self-directed inhaler skill training sessions through the virtual Teach-To-Goal (V-TTG) intervention I developed and tested during my K23 and, second, a handheld lung function device to provide physiologic feedback and capture medication adherence called SpiroPD. TTG is a patient-centered strategy that uses cycles of assessment and demonstration tailored to patients' self-management needs; my research shows *in-person* TTG is effective for teaching inhaler technique and reduces acute care utilization. Virtual-TTG delivers the key features of TTG using virtual patient-directed lessons through novel adaptive technology that provides tailored self-assessment and training. My studies demonstrate participants' willingness to use V-TTG at-home for post-discharge booster education and show that V-TTG is effective and may be non-inferior to *in-person* TTG in significantly reducing inhaler misuse among *hospitalized* patients. However, it remains unknown whether *at-home* V-TTG sessions will maintain self-management skills over the longer term and how direct physiologic lung monitoring support can impact medication adherence. The proposed studies will determine whether combining *at-home* skill training with objective measurements of lung function and adherence monitoring through the BREATHES Program improves self-management skills and medication adherence in the first 30 days after hospitalization for COPD.

## PURPOSE & HYPOTHESIS

Our central hypothesis is that patients hospitalized for COPD who subsequently complete the *at-home* BREATHES Program with V-TTG skill training and SpiroPD adherence support will retain increased medication knowledge, skill, self-efficacy, and adherence that otherwise decays substantially by 30 days post-discharge. To test this hypothesis, I propose the following specific aims:

**SA1. Determine the feasibility of, adherence to, and efficacy of *at-home* V-TTG for ongoing inhaler skill training.** Hypothesis: Participants who complete both *in-hospital* and *at-home* V-TTG will have a significantly increased likelihood of demonstrating effective respiratory inhaler technique within 30 days after hospital discharge compared to *in-hospital* technique.

**SA2. Determine the feasibility of, adherence to, and efficacy of at-home SpiroPD for COPD medication adherence support.** Hypothesis: Participants' use of SpiroPD (PMD Healthcare) will significantly improve their COPD medication adherence.

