## Study Schema

Table 1: Data Collection Tools		Hospital	Home	30-day
V-TTG adherence	Smart Sparrow platform data capture	-	X	-
Inhaler technique	Validated inhaler checklists	X	-	X
Inhaler knowledge, efficacy, skills	Inhaler step knowledge , applied inhaler use skill , and attitudes for inhaler self-efficacy assessed through short-answers.	X	X	X
Lung function	KoKo® portable spirometer: lung function (FEV1 %predicted). Handheld SpiroPD device (up to daily, at home)	X X	- X	X X
Treatment Adherence	Self-reported: Medication adherence report scale (MARS); dose-counter on applicable devices; optional medication diary on the SpiroPD device Objective: Propeller Health® Bluetooth devices.	X -	- X	X X
Self-efficacy	"I am confident that I know how to use [inhaler] correctly, (5-point scale).	X	X	X
Quality of life (QOL)	The Airway Questionnaire (AQ-20) 20-item tool assesses effect of current symptoms in everyday life for patients with COPD.	X	-	X
Symptoms	Modified Borg Dyspnea Scale; COPD Severity Score.	X	-	X
Health Literacy	Short Test of Functional Health Literacy in Adults: 36 item tool.	X	-	X

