## **TYPE AND NUMBER OF EXPERIMENTAL SUBJECTS**

We will enroll 70 study participants from patients admitted to the University of Chicago Medicine. Only 30 of these 70 subjects will utilize the Propeller Health device to objectively measure medication adherence. This subset of 30 patients will be chosen based on the patients' prescription of a Propeller-compatible inhaler device (as not all inhalers will be compatible with this technology) as well as their willingness to verbally assent to this portion of the study.

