## **STATISTICAL ANALYSES**

We will use means, medians, proportions, scatterplots, and histograms to describe the data. We will test for group differences using the *t*-test, the Wilcoxon rank sum test, Pearson's chi-squared test, or Fisher's exact tests, as appropriate. The primary outcomes for Aim 1 are at-home V-TTG adherence and inhaler technique and for Aim 2, at-home lung function testing adherence and medication adherence. McNemar's chi-squared tests will be used to compare 30 day post-discharge vs. pre-discharge adherence to the devices, prevalence of inhaler misuse ( $\leq 10/12$  steps correct), and medication adherence. Secondary outcomes will include change in

self-efficacy for inhalers, symptom burden, self-reported utilization of health care services, and QOL. A two-tailed p-value less than 0.05 will define statistical significance.

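### One-arm before-after tests of a bundled programme cannot show separate efficacy of V-TTG (SA1) or SpiroPD (SA2), nor that decay was prevented

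*Combined protocol and SAP*

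**What the plan says.** Under PURPOSE & HYPOTHESIS, SA1 seeks the feasibility of, adherence to and efficacy of at-home V-TTG. SA2 seeks the same for SpiroPD, ending in the "efficacy of at-home SpiroPD for COPD medication adherence support", and its hypothesis credits use of SpiroPD by name with improving medication adherence. The central hypothesis is that the programme preserves knowledge, skill, self-efficacy and adherence "that otherwise decays substantially by 30 days post-discharge".

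The design has one group: "We will enroll 70 study participants from patients admitted to the University of Chicago Medicine". BACKGROUND describes a single package: "BREATHES will include two main components", namely V-TTG and SpiroPD. Data Collection Time Points adds in-person TTG in hospital and text reminders. No control, randomisation, staggered start or historical comparator is described.

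STATISTICAL ANALYSES states that McNemar's "chi-squared tests will be used to compare 30 day post-discharge vs. pre-discharge adherence to the devices", and also inhaler misuse and medication adherence. Symptom burden and quality of life are secondary outcomes. The general rule is: "A two-tailed p-value less than 0.05 will define statistical significance". No passage limits the efficacy wording or discusses confounding or regression to the mean.

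**The concern.** Efficacy of a component means the difference between outcomes with it and without it. Here nobody goes without either component, so the data contain no such contrast. A significant McNemar result would show that something changed between hospital and day 30. It would not show that SpiroPD, or at-home V-TTG, caused the change.

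The same gap affects the retention claim. The plan expects decay without the programme, but this study does not measure how much decay there would have been.

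At stake is how the result will be read. Under the present aims, a p-value below 0.05 would be reported as evidence that a particular device or module works.

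**Working it through.** The documents state no power, effect size, discordance rate or dropout, so there is no figure to reproduce. The attribution point follows from the text alone. The calculations only show scale.

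**Step 1. What each comparison contains.**

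| Comparison | What changes between the two assessments |
|---|---|
| Pre-education baseline to day 30 | In-person TTG, at-home V-TTG, SpiroPD, reminders, time |
| Post-education assessment to day 30 | At-home V-TTG, SpiroPD, reminders, time |

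Neither row isolates V-TTG or SpiroPD. STATISTICAL ANALYSES says only pre-discharge, and SA1 says only in-hospital technique, so the plan does not fix which row applies. In the first row, the gain from in-person TTG (which BACKGROUND calls effective) could be credited to at-home V-TTG. In the second, decay works against a positive result, and a finding of no change still does not show that the programme prevented a loss.

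**Step 2. Medication adherence (SA2).** "Only 30 of these 70 subjects will utilize the Propeller Health device to objectively measure medication adherence". Table 1 in Study Schema shows Propeller data at home and at day 30 but none in hospital. Objective adherence therefore has no baseline to pair. The before-after comparison rests on the measures in the self-report row (MARS, dose counter, optional diary).

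**Step 3. McNemar with no effect of V-TTG or SpiroPD.** Inputs: n = 70 and two-sided 0.05 (documents); proportion discordant D and net improvement S from other causes (assumptions).

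- Proportion improving = (D + S)/2; proportion worsening = (D − S)/2.
- The test rejects when (b − c)²/(b + c) > 3.84, where b and c are the numbers improving and worsening.
- Example: D = 30%, S = 15 points gives 22.5% and 7.5%. In 70 pairs the expected counts are 15.75 and 5.25, and 10.5²/21 = 5.25, which is above 3.84.

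Exact rejection probabilities, summed over the binomial distribution of discordant pairs (continuity-corrected in brackets):

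| Net shift | D = 30% | D = 40% |
|---|---|---|
| 0 | 5% (3%) | 5% (3%) |
| 10 points | 34% (25%) | 27% (20%) |
| 15 points | 66% (56%) | 53% (44%) |
| 20 points | 91% (85%) | 79% (71%) |

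With no shift the test keeps its nominal level. The fault is the missing counterfactual, not the test.

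**Step 4. Symptoms and quality of life (secondary).** Table 1 schedules the "Modified Borg Dyspnea Scale; COPD Severity Score" and the AQ-20 in hospital and at day 30. The plan names no test for their change; a paired t-test is assumed here. With a recovery of d SDs of the change and no programme effect, the noncentrality is d√n. At n = 70, √n = 8.37, so d = 0.1 gives 0.84 and d = 0.5 gives 4.18, against a critical value of 1.99. The n = 56 column assumes 20% loss (70 × 0.8).

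| d (assumed) | n = 70 | n = 56 |
|---|---|---|
| 0.1 | 13% | 11% |
| 0.2 | 38% | 31% |
| 0.3 | 70% | 60% |
| 0.5 | 98% | 96% |

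**The case against.** A single-arm pilot is a legitimate design. BACKGROUND and the central hypothesis already frame the question as one about the combined programme, and SA1's hypothesis is already a within-person comparison. All of that stands, and it is why the remedy is wording. It does not rescue the aim statements, which name each component separately, or the SA2 hypothesis, which credits SpiroPD.

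A reader might infer that natural recovery from the admission would by itself make the efficacy endpoints significant. The documents do not support this. Those endpoints are inhaler technique and medication adherence, and BACKGROUND describes drift the other way after discharge: technique is lost quickly and complex regimens are hard to follow. Recovery bears on symptoms and quality of life, which are secondary and appear in neither aim. Even there its size is unknown. Inclusion requires a COPD diagnosis, not an exacerbation as the reason for admission, and the AQ-20 asks about everyday life. The plan names no test for these changes, and the significance rule is a general definition.

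A reader might also infer that the trial would declare a SpiroPD effect on adherence even if the whole programme did nothing. Nothing in the documents shows adherence rising unaided. The supportable statement is narrower: if adherence rises, the data cannot say that SpiroPD was the cause.

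**Conclusion.** The point holds for the efficacy part of SA1 and SA2 and for the claim that decay is prevented. That conclusion rests only on the design as described: one arm, one bundle, no comparator. It needs no assumed numbers.

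The illustrative sizes do rest on assumptions. With 70 pairs, a net shift of 10 to 20 points from other causes gives a significant uncorrected McNemar test in 27% to 91% of trials, for 30% to 40% discordance. For symptoms and quality of life, recovery of 0.1 to 0.5 SD of the change gives 13% to 98% at n = 70, or 11% to 96% at n = 56. That range is too wide to be more than a caveat on secondary outcomes.

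It would be too strong to call the aims as a whole undeliverable. Feasibility and adherence to the programme can be described in one arm. Nor does the point require a control group. With 35 per arm, power for 50% against 30% (assumed rates) would be about 40%, and 80% power would need 93 per arm.

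**What to change.** 1. **PURPOSE & HYPOTHESIS.** In SA1 and SA2, replace efficacy of at-home V-TTG and of SpiroPD with within-person change under the combined BREATHES programme. State the SA2 hypothesis for the programme, not for SpiroPD alone. Add that decay without the programme is not observed in this study. Reconcile SA1's reference to in-hospital V-TTG with Data Collection Time Points, which describes in-person TTG plus training in how to use V-TTG.
2. **STATISTICAL ANALYSES, inhaler misuse.** Name the post-education in-hospital assessment as the comparator when the question is retention at home, and give the paired difference with a 95% CI. Report any change from the pre-education baseline as the effect of the whole package, including in-person TTG. Confirm that the inhaler checklist is scored after education: the protocol does not list the contents of that assessment, and Table 1 has a single hospital column.
3. **STATISTICAL ANALYSES, secondary outcomes (minor).** Report symptom-burden and quality-of-life change as mean change with 95% CI, labelled as including any recovery from the index admission and not as evidence of a programme effect.

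The cost is wording, plus a checklist score after education if that is not already planned. The downside is a more modest claim.

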## METHODS OVERVIEW

We will voluntarily enroll 70 inpatients admitted to the University of Chicago Medicine over the course of 12 months into the at-home BREATHES Program. After obtaining informed consent, participants will complete in-hospital skills, lung function, and medication adherence assessments followed by the BREATHES at-home V-TTG inhaler learning program with self-monitoring and adherence support through the SpiroPD device. Participants will be trained on V-TTG and SpiroPD use in the hospital. The V-TTG intervention uses novel adaptive learning features that allow learners to participate in tailored educational sessions. They will begin every-other-day lung function assessments using the SpiroPD device in the hospital and continue on discharge. At 48-72 hours after discharge, participants will receive a unique username and password to complete the at-home V-TTG sessions on any of their own desktop or handheld devices; they will complete the V-TTG session at least one time in the first 30 days. Participants will receive reminders for completion of the V-TTG inhaler training and daily lung function monitoring via text messaging Adherence to the at-home V-TTG session (captured through the Smart Sparrow platform), lung function monitoring (captured via the SpiroPD device), and objective inhaler medication adherence (captured via Propeller Health Bluetooth objective monitoring; only 30 of these 70 patients will have objective medication adherence captured) will be assessed throughout the 30-days after discharge via the HIPAA compliant interface. Participants will return at 30 days post-hospital discharge for an in-person evaluation of their inhaler skills, lung function, and acute care utilization.

## RECRUITMENT

Admission logs (EPIC) at the University of Chicago will be examined each day to screen for potentially eligible inpatients. The treating physician will be contacted for verbal assent using standardized text. Among patients whose physician provides assent, medical records will be reviewed to ascertain eligibility and informed consent will be sought from eligible patients. Approximately 70 patients will be recruited at the University of Chicago Medicine over 12 months.

## Study Schema

Table 1: Data Collection Tools		Hospital	Home	30-day
V-TTG adherence	Smart Sparrow platform data capture	-	X	-
Inhaler technique	Validated inhaler checklists	X	-	X
Inhaler knowledge, efficacy, skills	Inhaler step knowledge , applied inhaler use skill , and attitudes for inhaler self-efficacy assessed through short-answers.	X	X	X
Lung function	KoKo® portable spirometer: lung function (FEV1 %predicted). Handheld SpiroPD device (up to daily, at home)	X X	- X	X X
Treatment Adherence	Self-reported: Medication adherence report scale (MARS); dose-counter on applicable devices; optional medication diary on the SpiroPD device Objective: Propeller Health® Bluetooth devices.	X -	- X	X X
Self-efficacy	"I am confident that I know how to use [inhaler] correctly, (5-point scale).	X	X	X
Quality of life (QOL)	The Airway Questionnaire (AQ-20) 20-item tool assesses effect of current symptoms in everyday life for patients with COPD.	X	-	X
Symptoms	Modified Borg Dyspnea Scale; COPD Severity Score.	X	-	X
Health Literacy	Short Test of Functional Health Literacy in Adults: 36 item tool.	X	-	X

## **Data Collection Time Points**

1. *In-Hospital Baseline Assessments*. Research Assistant (RA) will assess participants' baseline inhaler technique, inhaler self-efficacy, lung function, and self-reported adherence to their treatment regimen.

2. *In-Hospital Education*: Research Assistant (RA) provides in-person TTG inhaler training and training on how to use the V-TTG and lung function monitoring at home.

3. *In-Hospital Post-Education Assessments*. RA will obtain post-education assessments.

4. *Post-Discharge At-Home BREATHEs Program with V-TTG education and lung function monitoring*. The participant will complete up to daily lung function (goal of every other day) and medication adherence diaries using the SpiroPD device. The RA will give a unique username and password to each participant to access the V-TTG inhaler training after they have been discharged home. The V-TTG should be completed at least once within the first 30 days after discharge. The RA will send up to three reminders for completion of the lung function monitoring and V-TTG via text messaging. Participants will use their own device (tablet, laptop or desktop computer, or smartphone) for V-TTG use at home. For some patients, data will be collected each time they use their inhaled medication as prescribed. This data will be collected automatically when medication is utilized via a Propeller Health device attached to the inhaler. Patients should use their medication as they are instructed by their provider; no specified usage will be provided by the research team. Only data from regular use will be collected for this portion of the study.

5. *Post-Discharge Assessments*. Thirty days (+/-7 days) after discharge, participants will return for an in-person study visit to assess inhaler technique, adherence measures, lung function, and other assessments.

## **Device Data Collection**

The SpiroPD device will record participant use and lung function scores. These measurements are stored in a HIPAA compliant server over wifi and are available to the participant and research team. Data from the V-TTG educational modules will be collected via the Smart Sparrow platform. For a subset of approximately 30 patients, a device by Propeller Health will measure objective medication use and adherence. This device will collect only use of an inhaler medication and does not require the participant to use their treatment any differently than prescribed by the clinician. This data will be stored in a HIPPA compliant server only available to the research team.

## **Survey Data Collection**

Trained research staff will assess the following at the initial enrollment and the 30-day follow-up visit:

- Demographics
- Self-reported treatment adherence
  - o MARS
- Self-reported self-efficacy (5-point Likert scale)
- Quality of Life
  - o The Airway Questionnaire (AQ-20) 20-item tool assesses effect of current symptoms in everyday life for patients with COPD
- Symptoms
  - o Modified Borg Dyspnea Scale

- COPD Severity Tool
- Health Literacy
  - Short Test of Functional Health Literacy in Adults: 36 item tool.

## **Spirometry**

Spirometry will be performed during the initial visit and during the follow up visit using the portable KoKo spirometer and the SpiroPD device.

## **DURATION**

Participants will be enrolled in the at-home BREATHES Program for 30 days after discharge from the hospital. They will be in the study for 30 days (with a window of +/- 1 week for the 30 day visit) from the time of enrollment.

## **LOCATION**

The study will take place at the University of Chicago Medicine as well as at patient homes.

## **TYPE AND NUMBER OF EXPERIMENTAL SUBJECTS**

We will enroll 70 study participants from patients admitted to the University of Chicago Medicine. Only 30 of these 70 subjects will utilize the Propeller Health device to objectively measure medication adherence. This subset of 30 patients will be chosen based on the patients' prescription of a Propeller-compatible inhaler device (as not all inhalers will be compatible with this technology) as well as their willingness to verbally assent to this portion of the study.

### **Inclusion Criteria**

1. Age 18 years and older
2. Physician-diagnosed COPD (prior to or during hospitalization)
3. Owns a wifi-enabled device (desktop, laptop, tablet, smartphone, etc.)
4. Discharged with a rescue and/or controller MDI
5. Visual acuity of at least 20/50 in at least one eye (with or without corrective lens provided by the research team for study purposes)

### **Exclusion Criteria**

1. Currently in an intensive care unit
2. Physician declines to provide consent
3. Patient unable to provide consent (e.g., history of cognitive impairment, unable to understand English) or declines to provide consent

## **STATISTICAL ANALYSES**

We will use means, medians, proportions, scatterplots, and histograms to describe the data. We will test for group differences using the *t*-test, the Wilcoxon rank sum test, Pearson's chi-squared test, or Fisher's exact tests, as appropriate. The primary outcomes for Aim 1 are at-home V-TTG adherence and inhaler technique and for Aim 2, at-home lung function testing adherence and medication adherence. McNemar's chi-squared tests will be used to compare 30 day post-discharge vs. pre-discharge adherence to the devices, prevalence of inhaler misuse ( $\leq 10/12$  steps correct), and medication adherence. Secondary outcomes will include change in

self-efficacy for inhalers, symptom burden, self-reported utilization of health care services, and QOL. A two-tailed p-value less than 0.05 will define statistical significance.

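### Does the absence of a named paired test put the secondary analyses of change in self-efficacy, symptoms and quality of life at risk?

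*Combined protocol and SAP*

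**What the plan says.** The design has a single group: METHODS OVERVIEW puts all 70 participants into the same home programme. Under Survey Data Collection, "Trained research staff will assess the following at the initial enrollment and the 30-day follow-up visit", and the list that follows includes self-efficacy, the AQ-20, the Modified Borg scale and a COPD severity tool. The self-efficacy item in Table 1 (Study Schema) reads "I am confident that I know how to use [inhaler] correctly, (5-point scale", so it is ordinal with five levels.

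STATISTICAL ANALYSES contains three relevant statements.

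- A general sentence on tests: "We will test for group differences using the *t*-test, the Wilcoxon rank sum test", then Pearson's chi-squared and Fisher's exact tests, with the choice left to suitability. The groups are not named, and the t-test is not labelled paired or unpaired.
- A sentence on before-and-after comparison: McNemar's "chi-squared tests will be used to compare 30 day post-discharge vs. pre-discharge adherence to the devices", and likewise for inhaler misuse and medication adherence.
- A list of secondary outcomes expressed as change in "self-efficacy for inhalers, symptom burden, self-reported utilization of health care services, and QOL". No test is attached to it.

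The significance rule is "A two-tailed p-value less than 0.05 will define statistical significance". The documents give no power calculation, effect size, standard deviation, within-person correlation or expected dropout.

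**The concern.** The secondary scores are within-person quantities, yet for non-binary data the section names only an unlabelled t-test and the rank sum test. The rank sum test assumes independent samples. The one explicitly paired method, McNemar's test, is for binary data and is assigned to other outcomes. An analyst who wanted a rank method for the 5-point item and took the list literally would find only the rank sum test.

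Applied to the in-hospital and 30-day scores of the same people, that test ignores the pairing. If repeat scores are positively correlated, which is plausible, its standard error is too large and a real change could be missed. Self-efficacy also appears in the central hypothesis under PURPOSE & HYPOTHESIS, so a false null there would be noticed.

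**Working it through.** **Inputs.** From the documents: n = 70, two-sided alpha 0.05. Assumed, because the documents are silent: correlation rho of 0, 0.3, 0.5 or 0.7; a change d of 0.3 to 0.5 SD; 70 complete pairs, or 56 (70 × 0.8, a 20% loss). The plan has no figure of its own to reproduce.

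**Step 1: cost of ignoring the pairing.** In SD units, an unpaired test uses SE = sqrt(2/n). The true SE of the mean change is sqrt(2(1 − rho)/n). The ratio is 1/sqrt(1 − rho), and the actual type I error is 2 × (1 − Φ(1.96/sqrt(1 − rho))).

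At rho = 0.5, n = 70, d = 0.4, by normal approximation:
- SE used by the unpaired test: sqrt(2/70) = 0.169. True SE: sqrt(1/70) = 0.1195. Ratio 1.41.
- Type I error: 2 × (1 − Φ(2.77)) = 0.6%.
- Paired power: Φ(0.4/0.1195 − 1.96) = Φ(1.39) = 92%.
- Unpaired power: Φ((0.4 − 1.96 × 0.169)/0.1195) = Φ(0.57) = 72%.

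With t rather than normal critical values these become 91% and 71%. The full range, 70 pairs and d = 0.4:

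| rho | SE ratio | Actual type I error | Paired t power | Unpaired t power |
|---|---|---|---|---|
| 0 | 1.00 | 5% | 65% | 65% |
| 0.3 | 1.20 | 1.9% | 80% | 68% |
| 0.5 | 1.41 | 0.6% | 91% | 71% |
| 0.7 | 1.83 | 0.03% | 99% | 76% |

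At rho = 0.5 the gap is 70% v 39% for d = 0.3 and 98% v 92% for d = 0.5. With no correlation there is no loss. With positive correlation the error is conservative.

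**Step 2: does the missing signed-rank test matter?** A 5-point item was simulated from a latent bivariate normal, cut at −1.5, −0.75, 0 and 0.75, with a latent shift of 0.4 SD and 70 pairs (2,000 replicates; 3,000 for the rank sum column; Monte Carlo SE about 1 point).

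| rho | Signed-rank | Paired t | Rank sum |
|---|---|---|---|
| 0 | 58% | 58% | 59% |
| 0.3 | 72% | 73% | 60% |
| 0.5 | 83% | 84% | 62% |
| 0.7 | 95% | 96% | 65% |

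With 56 pairs at rho = 0.5: signed-rank 75%, paired t 76%, rank sum 51%. A second simulation with slightly different cut-points (2,500 replicates, 70 pairs, rho = 0.5) gave 82.7%, 83.3% and 61.1%. A t-test on the differences therefore does as well as the signed-rank test, even on a five-level item.

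**Step 3: does the plan call for the unpaired analysis?** Set the three statements side by side. The sentence naming the rank sum test concerns differences between groups and leaves the choice to suitability. The sentence comparing 30 days with before discharge is separate and uses a paired test. The secondary outcomes are worded as change. A one-sample t-test on a change score is the paired t-test, so a valid method is already on the list. The rank sum test remains valid for comparing patients with one another, including comparing change scores between subgroups. Nothing in the section assigns it to the paired scores.

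**The case for a change.** The best case for acting is that a plan should lead two analysts to the same analysis. The authors named a paired test for the binary outcomes and none for the scores, so pairing cannot be strictly inferred. The freedom to choose a suitable test runs only over the tests listed, and no paired rank test is among them. With at most 70 pairs, about 20 points of power could be lost at a moderate correlation, and the remedy is a few sentences.

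Part of this stands. The section does not say which test will be used for these changes or which groups the t-test and rank sum test compare, and no other section supplies it. The arithmetic is also right. But the power loss belongs to an analysis that the plan does not specify and that a competent analyst would not choose for scores taken twice on the same people. The authors' own use of McNemar's test shows that they recognised the pairing.

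The fuller remedy also reaches past the gap. Restricting to complete pairs is a missing-data decision. Comparing monitored with unmonitored participants ("Only 30 of these 70 subjects will utilize the Propeller Health device to objectively measure medication adherence") is not a planned analysis. Utilization raises a different matter, since METHODS OVERVIEW places it at the 30-day "in-person evaluation of their inhaler skills, lung function, and acute care utilization" and Table 1 shows no baseline for it.

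**Conclusion.** The concern does not call for a change. What remains is missing detail that analysts fill sensibly: scores taken twice on the same people, with change as the outcome, are analysed as pairs. Done that way, following the plan gives sound results, with no material loss from using the t-test instead of the signed-rank test on the 5-point item (differences of about one point or less across correlations of 0 to 0.7).

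The potential loss, from nothing at zero correlation to about 31 points at 0.3 SD and correlation 0.5 (70% v 39%), and larger still at higher correlations, arises only if the pairing is ignored. Every input to it except n and alpha is assumed. Even then it would affect secondary outcomes only, would not inflate false positives under positive correlation, and would leave the McNemar comparisons untouched. The conclusion rests on reading the unlabelled t-test as paired for change scores, which the wording permits and the before-and-after sentence supports.
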